5.6 Reporting Conventions

- P-value is rounded to four decimal places.
- If the calculated p-value is less than 0.0001, offer it as < 0.0001.
- Descriptive statistic (mean, standard deviation, median, minimum, maximum, percentage) is rounded to two decimal places.

6. Evaluation of Study Data

The analysis dataset applied to each analysis item is as follows.

| Analyses | Safety Analysis Set | Non-Safety Analysis Set |
|----------------------------------|---------------------|-------------------------|
| Special Group | ✓ | |
| Demographics | ✓ | |
| Medical History | ✓ | |
| Medication | ✓ | |
| Vaccination | ✓ | |
| Cervarix vaccination Information | ✓ | |
| Safety Evaluation | ✓ | ✓ [†] |

[†] Only 6.8.4 analysis

6.1 Disposition of Subjects

For the subjects who participated in a PMS, the following analysis group information will be presented as frequency and percentage (%)

- Number of enrollment subjects
- Number of Cervarix vaccination subjects
- Number of subjects in safety analysis set
- Number of subjects and reasons in non-safety analysis set

6.2 Special Group

In standard for re-examination of new drugs, etc.(2012), the point to reported is defined as follow. (Chapter 2, no 3).

(2) Investigation of specific subjects

Investigation for specific subjects includes investigation for children, elderly, pregnant women, subjects with renal failure, subjects with hepatic failure, and other specific subjects.

For investigation of such items, if there are specific subjects in general Clinical Experience Program, they may be extracted for investigation. For example, if 'Attention shall be paid to administration to children' is mentioned in approvals (precautions) and there are children in the

results of general Clinical Experience Program, investigation shall be conducted for the subjects.

According to the above, a special group is defined as follows and descriptive statistics is presented.

- Pediatric group ^a
- Geriatric group ^b
- Pregnancy group
- Renal disease group
- Liver disease group

^a Pediatric subject: subjects who under 18 years old

^b Geriatric subject: subjects who 65 years old or more (Not applicable)

6.3 Demographics

The following continuous data will be summarized with descriptive statistics.

- Age
- Height
- Weight
- BMI

The following categorical data will be summarized with descriptive statistics.

- Age group
- Gender
- Ethnicity

6.4 Medical History

The following categorical data will be summarized with descriptive statistics.

- Past medical history ^a
- Current medical history ^b

^a Past medical history: In case of conditions, signs or symptoms prior to the start of the study

^b Current medical history: In case of conditions, signs or symptoms lasting after the start of the study

In re-examination report, the past / current medical history could be classified by main title by disease of Korean Standard Classification of Disease (KCD).

If one subjects has two or more medical history in one category, it will be analyzed as one subject within the category. Also, the one subject may appear as a duplicate in different categories.

6.5 Medication

The following categorical data will be summarized with descriptive statistics. The concomitant medication during the 30-day (Day 1 to Day 30) after each vaccine dose will be also tabulated using descriptive statistics.

- Prior medication ^a
- Concomitant medication ^b

^a Prior medication: In case of that has/have been administered medication(s)/treatment(s) within 30 days (day -29 to day 1) prior Cervarix vaccination

^b Concomitant medication: In case of that has/have been administered medication(s)/treatment(s) within 30 days (day 1 to day 30) after Cervarix vaccination

In re-examination report, the prior / concomitant medication could be classified by main category and sub category of Korea Index of Medical Specialties (KIMS).

If one subjects has two or more medication in one category, it will be analyzed as one subject within the category. Also, the one subject may appear as a duplicate in different categories.

6.6 Vaccination

The following categorical data will be summarized with descriptive statistics. The concomitant vaccination during the 30-day (Day 1 to Day 30) after each vaccine dose will be also tabulated using descriptive statistics.

- Prior vaccination ^a
- Concomitant vaccination ^b

^a Prior vaccination: In case of that has/have been administered any vaccine(s) other than Cervarix within 30 days (day -29 to day 1) prior Cervarix vaccination

^b Concomitant vaccination: In case of that has/have been administered any vaccine(s) other than Cervarix within 30 days (day 1 to day 30) after Cervarix vaccination

In re-examination report, the prior / concomitant vaccination could be classified by main category and sub category of Korea Index of Medical Specialties (KIMS).

If one subjects has two or more vaccination in one category, it will be analyzed as one subject within the category. Also, the one subject may appear as a duplicate in different categories.

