**6.4.10. Distribution, return and transcription of diary cards**

The physician will provide the diary card to the subjects or subject's parent(s)/LAR(s) to record e. g. Medication taken, AE, SAE, and pregnancy until next visit/contact. The subjects or subject's parent(s)/LAR(s) will be instructed to return the completed diary card to the physician at the next visit/contact.

Collection and verification of the completed diary card will take place during discussion with the subjects or subject's parent(s)/LAR(s) at the subsequent visit/contact. Any unreturned diary cards will be sought from the subjects or subject's parent(s)/LAR(s) through telephone call(s) or any other convenient procedure. The Physician will transcribe the collected information into the CRF in English

After each vaccination, diary cards will be provided to the subjects or subject's parent(s)/LAR(s) to record any AEs (i.e. on the day of vaccination and during the next 29 days) occurring after vaccination. The subjects or subjects' parent(s)/LAR(s) will be instructed to return the completed diary card to the physician on their next PMS visit or provide details during the telephonic interview from physicians or by postal mail. Site staff will try to contact subject or subject's parent(s)/LAR(s) through telephone call(s) (**at least 3 attempts**) for any unreturned diary for follow up. Information collected will be treated confidentially and for the purpose of reporting SAE(s) to MFDS (Korea), and for publication, if required.

Collection of pregnancy outcome information from pregnant subjects who received *Cervarix*, at 6-8 weeks after the Estimated Date of Delivery, if possible.

**CONFIDENTIAL**208710 (EPI-HPV-077 VS KR PMS)  
Protocol Amendment 1 Final**6.4.11. Recording of AEs, ADRs and SAEs**

Refer to Section 8.3 for procedures for the Physician to record AEs, ADRs and SAEs and to Section 8.3 for guidelines on how to report these AEs /ADRs /SAEs to GSK Biologicals.

The subjects or subjects' parent(s)/LAR(s) will be instructed to contact the physician immediately should the subjects manifest any signs or symptoms they perceive as serious.

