## 7.4. Concomitant medication/vaccination (Amended: 14 May 2018)

All concomitant vaccinations according to local practice are allowed during the PMS. *Collected information for concomitant medication/vaccination such as trade/generic name, route, frequency, total daily dose (dose, unit), start date, end date, indication etc. needs to be recorded in the CRF.* The medication/vaccination history (within 30-days prior to the *Cervarix* vaccination) should be documented in the CRF. For subjects who have received any of their dose/s of *Cervarix* outside the PMS and appear for the subsequent dose/s in this PMS, previous *Cervarix* vaccination history will be reported starting at first visit onwards irrespective of the dose subject has appeared for in the PMS. (Refer to the [Table 1](#)).

At each PMS visit/contact, the physician should question the subjects or subject's parent(s)/LAR(s) about any medication taken and vaccination received by the subject.

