### 7.4.2. Time window for recording concomitant medication/vaccination in the CRF

- All concomitant medications, with the exception of vitamins and/or dietary supplements, administered at ANY time during the period starting with the administration of each dose of *Cervarix* and ending 30 days (**Day 1 to Day 30**) after each dose of *Cervarix* must be recorded in the CRF.
- Any vaccine not foreseen in the PMS protocol administered in the period beginning 30 days (Day – **29** to Day **1**) preceding each dose of *Cervarix* and ending 30 (**Day 1 to Day 30**) days after each dose of *Cervarix* must be recorded in the CRF.

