### **8.3.2.3. Assessment of causality**

The Physician is obligated to assess the relationship between *Cervarix* and the occurrence of each AE/SAE. The Physician will use clinical judgement to determine the relationship. Alternative plausible causes, based on natural history of the underlying diseases, concomitant therapy, other risk factors and the temporal relationship of the event to the administration of *Cervarix* will be considered and investigated. The Physician will also consult the local Prescribing Information (Summary of Product Characteristics, SPC) to ensure an accurate assessment.

There may be situations when a SAE has occurred and the Physician has minimal information to include in the initial report to GSK Biologicals. However, it is very important that the Physician always makes an assessment of causality for every event prior to submission of the SAE to GSK Biologicals. The Physician may change his/her opinion of causality in light of follow-up information, and update the SAE information accordingly. The causality assessment is one of the criteria used when determining regulatory reporting requirements.

In case of concomitant administration of multiple vaccines, it may not be possible to determine the causal relationship of general AEs to the individual vaccines administered. The Physician should, therefore, assess whether the AE could be causally related to vaccination rather than to the individual vaccines.

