6.8.1 Summary of Adverse Events

The summary table of adverse events will be presented about the following items. The number of

subjects, incidence proportion, its 95% confidence interval and the number of adverse events will be presented in the summary table. The analysis of adverse event/serious adverse event during the 30-day (Day 1 to Day 30) after each vaccine dose will be also performed separately.

- Adverse event (AE) · Adverse drug reaction (ADR) ^a
- Serious adverse event · Serious adverse drug reaction
- Unexpected adverse event ^b · Unexpected adverse drug reaction
- Unexpected serious adverse event · Unexpected serious adverse drug reaction
- Unexpected non-serious adverse event ^c · Unexpected non-serious adverse drug reaction

^a Adverse drug reaction (ADR): Adverse event that the 'relate to Cervarix' is 'Certain', 'Probable / Likely', 'Possible', 'Conditional / Unclassified' and 'Unassessable / Unclassifiable'

^b Unexpected adverse event: Adverse event that is not included in the local product insert

^c Unexpected non-serious adverse event: Adverse event that is non-serious and not included in the local product insert

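### SAP 6.5 and 6.6 count Day 1 as both prior and concomitant, so one same-day vaccine or drug becomes two factors, and the ADR tables list no same-day split

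*SAP*

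**What the plan says.** Protocol 7.4 permits co-administration: "All concomitant vaccinations according to local practice are allowed during the PMS". Day 1 is the vaccination day itself, because the diary card in Protocol 6.4.10 covers events "on the day of vaccination and during the next 29 days".

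SAP 6.6 defines two classes. Prior vaccination is "any vaccine(s) other than Cervarix within 30 days (day -29 to day 1) prior Cervarix vaccination". Concomitant vaccination is "any vaccine(s) other than Cervarix within 30 days (day 1 to day 30) after Cervarix vaccination". SAP 6.5 uses the same two windows for medication. Section 7.2 codes each class as Yes/No, without a same-day category and without saying which dose the code refers to.

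Section 6.8.3 gives AE incidence with a 95% interval and a chi-square or Fisher test for each categorical factor in 6.2 to 6.7, which includes these four. Factors with p < 0.05 go into a multiple logistic model at the re-examination. Under 5.5 that model is not run if two or fewer factors are significant.

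On causality, Protocol 8.3.2.3 asks the physician, when several vaccines are given together, to "assess whether the AE could be causally related to vaccination rather than to the individual vaccines". The reason it gives concerns general AEs. The same section then puts the causality question for Cervarix alone. SAP 6.8.1 defines an ADR as an "Adverse event that the 'relate to Cervarix' is 'Certain', 'Probable / Likely', 'Possible" (or one of the two unclassified categories).

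**The concern.** The background-factor analysis is where the plan would show whether other vaccines or drugs contribute to reported events. If a same-day vaccine is coded as both prior and concomitant, a co-administration effect will also look like an effect of earlier vaccination, and the Yes groups no longer describe one kind of exposure.

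The stated objective is the safety of Cervarix. If, in co-vaccinated subjects, the relatedness answer can mean related to any vaccine given that day, the ADR rows need a companion figure free of same-day vaccines. The SAP text lists none.

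**Working it through.** **Inputs.** Windows: SAP 6.5 and 6.6. Meaning of Day 1: Protocol 6.4.10. Coding: SAP 7.2. Model condition: SAP 5.5. Data collected: Protocol 7.4. No co-administration rate is given in either document.

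**1. Day count.** With no Day 0, day -29 to day -1 is 29 days; adding Day 1 gives the stated 30. Day 1 to Day 30 is also 30. (With a Day 0 the prior window would be 31 days, which does not match.) The stated lengths therefore hold only with Day 1 in both windows: 30 + 30 = 60 class-days over 59 distinct days, and the overlap is Day 1 alone.

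**2. What each exposure does to the factors** (both taken around the same dose):

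| Other vaccine given | Prior | Concomitant |
|---|---|---|
| None in the window | No | No |
| Only day -29 to -1 | Yes | No |
| Only Day 1 | Yes | Yes |
| Only Day 2 to 30 | No | Yes |
| Before and after, not on Day 1 | Yes | Yes |

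Prior = Yes mixes earlier with same-day use. Concomitant = Yes mixes same-day with later use. Cross-tabulating the two would not isolate same-day use, because the last row is also Yes/Yes. Both No strata are free of same-day vaccines.

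**3. Model condition.** At least three significant factors are needed. One same-day exposure can supply two, so a single further factor is enough. The same holds for a drug given on Day 1.

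**4. Collinearity (illustration, assumed shares).** Let a be the share of subjects with a same-day vaccine only, b earlier only, c later only; P = a + b, C = a + c. Then

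phi = (a − P·C) / √[P(1 − P)·C(1 − C)].

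With a = 0.05:

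- b = c = 0: P = C = 0.05, phi = (0.05 − 0.0025)/0.0475 = 1.00. Earlier-only use is 0% of Prior = Yes, and the model cannot hold both terms.
- b = c = 0.01: P = C = 0.06, phi = (0.05 − 0.0036)/0.0564 = 0.82. Earlier-only use is 0.01/0.06 = 17% of Prior = Yes.
- b = c = 0.05: P = C = 0.10, phi = (0.05 − 0.01)/0.09 = 0.44. Earlier-only use is 0.05/0.10 = 50%.

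**5. AEs versus ADRs.** Section 6.8.3 is written for all AEs, so AE incidence without a same-day vaccine can be read from a No stratum. ADRs are reported in 6.8.1 and 6.8.2, which list a breakdown by dose and by term but none by co-vaccination.

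**6. Causality wordings.** For general AEs under co-administration, Protocol 8.3.2.3 gives two targets: vaccination as a whole, then Cervarix. The SAP's ADR definition assumes the second. Nothing says which one the recorded answer reflects when another vaccine was given.

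**The case against.** The best defence is that the data are adequate and much of the separation is already planned. Other vaccines are recorded with details "such as trade/generic name, route, frequency, total daily dose (dose, unit), start date, end date, indication etc", AEs are tabulated by prior and by concomitant vaccination, concomitant vaccination is tabulated after each dose, and events are split by administration site. Section 6.8.3 also lets the analyst add or remove model factors. In a descriptive, non-comparative surveillance, no sample size or error rate depends on this point. All of that stands, with two limits. Removing a factor after seeing the results is not a rule for which one to remove, and the AE tabulations do not extend to ADRs.

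On causality, the instruction is limited to general AEs. The protocol's ADR definition is also deliberately wide: anything that cannot be ruled out counts, and the category for possible relation covers events that other medicines could explain. Counting ambiguous events as ADRs is therefore partly by design. That does not settle which product the answer refers to.

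The protocol uses the same overlapping windows for recording (7.4.2: "Any vaccine not foreseen in the PMS protocol administered in the period beginning 30 days"). For recording, the overlap is harmless; it matters only once the SAP turns the windows into separate factors. The words prior and after might be read as clock order on Day 1, but time of administration is not among the items listed in Protocol 7.4.

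A reader might also treat a vaccine given between two doses as a second double count. It is not an error: that vaccine does follow one dose and precede the next.

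**Conclusion.** The point holds as a definitional overlap of one day, with consequences for the factor analysis in 6.8.3, together with a missing ADR split and two causality wordings that conflict. The correlations of 0.44 to 1.00 rest on assumed shares and on both factors being taken around the same dose. The SAP does not state the latter, and the protocol is mixed: its Table 3 collects history at Visit 1 only, while 7.4.2 refers to each dose.

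Two stronger readings are not supported. One is that the surveillance cannot separate Cervarix reactions from those of co-administered vaccines. It can, because dates are collected and the No strata are clean for AEs; the gap is in the planned classes and ADR tables. The other is that ADR incidence is inflated by some stated amount. Neither the share co-vaccinated nor the share reacting is in the documents, and multiplying two assumed shares would overstate the effect, because a subject who already has an ADR adds nothing to a subject-level proportion. The size of any effect on ADR incidence is unknown.

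The statement about missing splits concerns the body of the SAP; the content of its mock-table appendix is not available to check.

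**What to change.** - **SAP 6.6, 7.2 and 6.8.3:** replace the two vaccination factors with three disjoint classes per dose: day -29 to -1 (29 days), Day 1, and Day 2 to 30. State how doses combine into a subject-level factor.
- **SAP 6.5:** adopt one non-overlapping rule for drugs given on Day 1. Which class takes Day 1 is a choice, since a prophylactic drug may be given before the dose on that day, but it should be one class only.
- **SAP 6.8.1 and 6.8.2:** beside the total, show ADR incidence for doses with no same-day vaccine and, to address carry-over, for doses with no other vaccine in the window. Give these by dose number, so that each subject counts at most once per interval, and state the denominator, because 5.5 now fixes it as the whole safety set.
- **Protocol 8.3.2.3 and SAP 6.8.1:** reconcile the two causality wordings with the ADR definition, and say what a recorded relation means under co-administration.

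The class and table changes need SAP wording and extra columns but no new data. The causality change needs a protocol clarification. The downside is smaller numbers, and so wider intervals, in the added columns.

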6.7 Cervarix Vaccination Information

The following continuous data will be summarized with descriptive statistics.

- Pre-vaccination body temperature

The following categorical data will be summarized with descriptive statistics.

- Vaccination history of prior Cervarix ^a
- Dose number of Vaccination history of prior Cervarix
- Total number of Cervarix vaccination in the PMS
- Order of Cervarix vaccination

Pre-vaccination body temperature will be presented per each visit.

^a vaccination history of prior Cervarix: In case of that has/have received one or two dose(s) of Cervarix before the enrollment

6.8 Safety Evaluation

Section 6.8.1 shall be conducted for both safety analysis set and non-safety analysis set. Section 6.8.2, 6.8.3 and 6.8.5 will be performed on the safety analysis dataset and section 6.8.4 will be performed on the non-safety analysis set.

6.8.1 Summary of Adverse Events

The summary table of adverse events will be presented about the following items. The number of

subjects, incidence proportion, its 95% confidence interval and the number of adverse events will be presented in the summary table. The analysis of adverse event/serious adverse event during the 30-day (Day 1 to Day 30) after each vaccine dose will be also performed separately.

- Adverse event (AE) · Adverse drug reaction (ADR) ^a
- Serious adverse event · Serious adverse drug reaction
- Unexpected adverse event ^b · Unexpected adverse drug reaction
- Unexpected serious adverse event · Unexpected serious adverse drug reaction
- Unexpected non-serious adverse event ^c · Unexpected non-serious adverse drug reaction

^a Adverse drug reaction (ADR): Adverse event that the 'relate to Cervarix' is 'Certain', 'Probable / Likely', 'Possible', 'Conditional / Unclassified' and 'Unassessable / Unclassifiable'

^b Unexpected adverse event: Adverse event that is not included in the local product insert

^c Unexpected non-serious adverse event: Adverse event that is non-serious and not included in the local product insert

6.8.2 Adverse Events by Preferred Term

All adverse events that occurred after the vaccination of Cervarix will be classified by terminology of System Organ Classes (SOC) and Preferred Term (PT) or Included Term (IT) of World Health Organization–Adverse Reaction Terminology (WHO-ART).

About the following items, adverse events of the subjects which occurred during or after the vaccination of Cervarix in accordance with SOC, PT or IT will be presented for the number of subjects, incidence proportion and its 95% confidence interval using exact method and the number of adverse events. At the time, even if one subject has 2 or more adverse events in one category, it will be analyzed as one within the category. Also, one subject may be presented as a duplicate in different categories.

- Adverse event · Adverse drug reaction
- Serious adverse event · Serious adverse drug reaction
- Unexpected adverse events · Unexpected adverse drug reaction
- Unexpected serious adverse events · Unexpected serious adverse drug reaction
- Unexpected non-serious adverse events · Unexpected non-serious adverse drug reaction

For all adverse events, the number of adverse events will be presented by following items. Additionally, all adverse events will be classified by System Organ Classes (SOC) and Preferred Term

(PT) or Included Term (IT) and presented as the number of each adverse events.

- Site
- Outcome
- Maximum intensity
- Relate to Cervarix
- Medically attended visit

Detailed adverse events will be listed by subjects for the following items.

- Serious adverse event
- Unexpected adverse event
- Unexpected serious adverse event
- Adverse event of subject with liver disease
- Adverse event of subject with renal disease
- Adverse event leading to withdrawal ^a

^a Adverse event leading to withdrawal: In case that 'Did the subject return for the visit?' is 'No' and major reason is 'Serious Adverse Event and/or Non-Serious related AE' in at least one visit

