#### **11.5.2. Analysis of safety**

Safety analysis based on total vaccinated cohort, will include all subjects who were vaccinated per product information and have completed 30-day follow-up after at least one dose, regardless of the number of dose. Analysis of AE/SAE data reported after each dose will be performed separately.

**CONFIDENTIAL**208710 (EPI-HPV-077 VS KR PMS)  
Protocol Amendment 1 Final**11.5.2.1. Within group assessment**

The AEs/ SAEs will be analysed in the PMS report according to the expectedness and unexpectedness criteria. (Refer to **GLOSSARY OF TERMS** for the definitions of expected AEs and unexpected AEs).

The number and percentage, with exact 95% confidence interval (CI), of any AEs occurring within 30 days (**Day 1 to Day 30**) will be tabulated, for each dose, for overall doses and by number of subjects. The same calculations will be done for any adverse events according to the severity and for those assessed as causally related to vaccination.

The verbatim reports of signs and symptoms will be matched and coded according to the appropriate WHO-ART Preferred Term. The PMS physician will review and confirm the appropriate WHO-ART Preferred Term by responding to data queries if any discrepancies are reported while coding. The percentage of subjects with AEs occurring within 30 days (**Day 1 to Day 30**) with its exact 95% CI will be tabulated by preferred term. Similar tabulation will be done for AEs with relationship to vaccination and for AEs rated as grade 3.

The number and percentage of subjects who received concomitant medication/ vaccination at least once during the 30-day (**Day 1 to Day 30**) follow-up period will be tabulated after each vaccine dose and overall, with exact 95% CI. Similar tabulations will be done for the number of subjects by types of medication/ vaccination during the entire PMS period.

The outcome of pregnancy (reported in the pregnancy report form) for subjects who become pregnant subjects during PMS will be presented, If possible.

Serious adverse events and withdrawals due to adverse events reported during the PMS period (each subject receiving the vaccine up to 30 days after the last dose) will be described in detail.

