2.1 Study Objective

To assess the safety of GSK Biologicals' HPV vaccine containing HPV-16/18 L1 virus-like particles (VLPs) and AS04 adjuvant, in terms of frequency and intensity of adverse events (AEs) and serious adverse events (SAEs) when administered according to the local Prescribing Information (PI).

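### SAP 6.8 specifies adverse event intensity only as event counts, so its text omits the subject percentages and exact intervals by severity that Protocol 11.5.2.1 requires

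*SAP*

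**What the plan says.** **Objective.** SAP 2.1 sets out to assess safety "in terms of frequency and intensity of adverse events (AEs) and serious adverse events (SAEs) when administered according to the local" prescribing information. Protocol section 2 has the same objective. Intensity is one of its two named dimensions.

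**Protocol 11.5.2.1.** The base analysis is "The number and percentage, with exact 95% confidence interval (CI), of any AEs occurring within 30 days", tabulated for each dose, over all doses and by number of subjects. The protocol continues: "The same calculations will be done for any adverse events according to the severity and for those assessed as causally related to vaccination". It then calls for the percentage of subjects with events, with exact 95% interval, by WHO-ART preferred term, and adds: "Similar tabulation will be done for AEs with relationship to vaccination and for AEs rated as grade 3".

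**SAP 6.8.1.** For each class of event, "subjects, incidence proportion, its 95% confidence interval and the number of adverse events will be presented in the summary table". There are ten classes: adverse events, serious, unexpected, unexpected serious and unexpected non-serious, each paired with the matching adverse drug reaction class. The section also asks for a separate analysis of adverse and serious adverse events after each dose.

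**SAP 6.8.2.** The same ten classes are tabulated by system organ class and preferred term, with subjects, proportion, exact interval and events. A different rule follows for site, outcome, maximum intensity, relationship and medically attended visit: "For all adverse events, the number of adverse events will be presented by following items". These are also broken down by system organ class and preferred term "and presented as the number of each adverse events".

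**SAP 7.2** lists mild, moderate and severe as the intensity categories and attaches no statistic to them.

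**The concern.** A count of events is not an incidence. One subject can contribute several severe events, through different symptoms after one dose or recurrence over up to three doses. A severity table of events alone does not tell the regulator what proportion of vaccinees had a severe reaction, or how precisely that proportion is known. The protocol planned both figures.

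The SAP separates subjects from events within 6.8.2 itself. For the ten classes, a subject with repeated events in a category counts once. For intensity, the unit is the event. The causally related part of the protocol sentence survives with subject percentages and intervals, and the severity part does not. SAP section 1 gives the protocol's method as its basis, and the SAP offers no reason for the difference.

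The term maximum intensity may mislead. In Protocol 8.3.2.2 it is the worst grade over the duration of one event, not a subject's worst grade over all events. Tabulating it therefore produces no subject-level summary.

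**Working it through.** **Step 1. Compare the texts.**

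| Analysis | Protocol 11.5.2.1 | SAP text |
|---|---|---|
| Any adverse event | n, %, exact 95% CI; per dose, all doses, by subject | 6.8.1: subjects, proportion, CI, events; also after each dose |
| Causally related | Same statistics | 6.8.1 and 6.8.2, as adverse drug reactions: subjects, proportion, CI, events |
| By severity | Same statistics | 6.8.2: number of events |
| Grade 3 by preferred term | % of subjects, exact 95% CI | 6.8.2: number of events, by intensity and preferred term |

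The rest of the SAP does not fill the last two rows. Section 6.8.3 is by baseline factor, 6.8.4 repeats the ten classes for the non-safety set, and 6.8.5 is by frequency category in the prescribing information. Section 5.5 says that intervals are exact but adds none for intensity. Section 5.3 provides frequency and percentage for categorical data. Applied to an event table, that gives a percentage of events, with neither a subject denominator nor an interval.

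**Step 2. Reproduce the protocol's own precision figures.** Inputs: n = 600 and the observed rates in Protocol Table 6 (section 11.2). The Clopper-Pearson limits for x subjects out of n are:

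- lower = 2.5% quantile of Beta(x, n − x + 1)
- upper = 97.5% quantile of Beta(x + 1, n − x)

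| Rate | x | Computed (%) | Table 6 (%) |
|---|---|---|---|
| 1% | 6 | 0.37 to 2.16 | 0.4 to 2.2 |
| 5% | 30 | 3.40 to 7.06 | 3.4 to 7.1 |
| 20% | 120 | 16.87 to 23.43 | 16.9 to 23.4 |

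All eight rows of Table 6 agree to one decimal. The exact subject-level interval is thus well defined and is the precision measure that the protocol planned.

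**Step 3. Show what an event count leaves open.** The documents give neither a severe-event rate nor a number of events per subject. The 30 grade 3 events below are an assumption, spread over different numbers of subjects out of 600.

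| Subjects | Events per subject | % of 600 | Exact 95% CI (%) |
|---|---|---|---|
| 30 | 30/30 = 1.0 | 5.00 | 3.40 to 7.06 |
| 20 | 30/20 = 1.5 | 3.33 | 2.05 to 5.10 |
| 15 | 30/15 = 2.0 | 2.50 | 1.41 to 4.09 |
| 6 | 30/6 = 5.0 | 1.00 | 0.37 to 2.16 |

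The overall count of severe events is 30 in every row.

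**Step 4. Check whether other specified outputs recover the figure.** The SAP 6.8.2 subject listings cover serious events, unexpected events, events in subjects with liver or renal disease, and events leading to withdrawal. An expected, non-serious grade 3 event in a subject without those conditions who did not withdraw because of it appears in none of them. Protocol 8.3.2.2 itself warns against confusing grade 3 with serious.

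**The case against.** The strongest objection is that the SAP's appendix of mock tables was not available. Shells often carry the subject and percentage columns, and SAP 7.1 sends additional calculation formulas to the tables. A subject-level intensity shell cannot be excluded. This stands, and it limits the point to what the SAP text specifies.

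Second, the SAP does not forbid the analysis. Event counts and subject percentages can both be produced without breaching either document. Protocol 11.4 requires departures from its statistical plan to be described and justified in the final report, so the protocol's requirement remains in force. A reader might infer that the SAP overrides the protocol, but the text shows only that it leaves out the subject-level part. It remains a departure, because the SAP sets out the intensity analysis with a different unit from the protocol's.

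Third, a reader might infer that half of the objective goes unanalysed. It does not: intensity is tabulated by events, overall and by preferred term. What is missing is the subject denominator and the interval.

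Fourth, the one-against-five events per subject contrast is an extreme. With 20 subjects the interval (2.05 to 5.10) overlaps the 30-subject interval (3.40 to 7.06). The example shows ambiguity, not an expected error.

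Finally, the study is descriptive with a single group, no decision rule depends on this table, and Protocol 11.4.1 includes individual data listings. The information is therefore not lost, but listings do not replace a required table.

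**Conclusion.** The point holds as an omission in the SAP text. Protocol 11.5.2.1 requires subject-level severity results with exact intervals and a grade 3 table by preferred term, while SAP 6.8 specifies intensity only as numbers of events. As written, that text does not yield the proportion of vaccinees with a severe adverse event or its precision.

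The size cannot be fixed from the documents. Under the assumed 30 events in 600 subjects, the proportion runs from 5.00% down to 2.50% at one to two events per subject, and to 1.00% at five. The conclusion rests on the visible SAP text, and a suitable shell in the appendix would reduce the point to aligning the wording. It merits correction because intensity is named in the objective and the repair is small. It does not threaten the study's data or conduct.

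**What to change.** - **SAP 6.8.1:** add subjects by maximum intensity (mild, moderate, severe), each counted once at the worst grade, with n, % and exact 95% interval, overall and per dose. The worst-grade rule is a proposal, since the protocol does not say how to count a subject with events of several grades. State the denominator for each table.
- **SAP 6.8.2:** add grade 3 adverse events by system organ class and preferred term, with number of subjects, % and exact 95% interval.
- Keep the event counts as an additional column.
- Check that the mock tables match. If a suitable shell already exists, refer to it in the text.

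Rows for grade 3 adverse drug reactions are optional, because Protocol 11.5.2.1 does not explicitly ask for them.

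The cost is SAP wording and a few table shells. Protocol 8.3.2.2 already has intensity assessed for every adverse event, so no new data are needed.
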